COMIRB Protocol

COLORADO MULTIPLE INSTITUTIONAL REVIEW BOARD
[name] [contact] [contact]

Protocol #: 20-1866

Project Title: Understanding Affective Processing of Scientific Evidence to Promote Informed Choice for Breast Cancer Screening

Principal Investigator: [name]

Version Date: 5.10.2021

I. Hypotheses and Specific Aims:

Cancer screening for the right patients at the right level of cancer risk can save lives. However, over the last several years most expert groups have de-intensified many screening recommendations as a result of emerging evidence of net harms for certain populations. Newer recommendations for mammography screening highlight a tailored approach based on age and risk and comorbidities, aiming to minimize harms and target women who could benefit the most.¹ Although there is still widespread disagreement about when and how frequently certain populations of women should receive breast screening, one point of agreement is that women should make an informed choice with their doctor about when to start, when to stop, and how frequently to screen.²⁻⁴

However, the change in emphasis from uniformly promoting mammography to promoting informed choice constitutes a medical reversal in the sense that this new message is very different from past messages and people's expectations.^{1,5-7} The result is a delicate situation in which there is need to convey the evidence to women, but also a need to do it in a way that maintains credibility and trust despite this reversal. Research suggests that many women react negatively to mammography evidence, responding with **Reactance** (e.g., "this is trying to manipulate me", "this is trying to ration healthcare"), **self-Exemption** (e.g., "this doesn't apply to me"), **Disbelief** (e.g., "you can't believe all the research"), or **Source derogation** (e.g., "I don't trust this source"),^{6,8,9} which we refer to together as **REDS**. These responses reflect different ways of rejecting of the evidence, stand in the way of informed choice, and could lead to distrust in future screening health messages.

AIM 1: Identify the prevalence and predictors of REDS in reaction to evidence about mammography benefits and harms, and consequences for decision-making and trust. Research has not yet systematically identified the proportion of women who respond negatively (vs. positively) to mammography evidence, or attempted to explain these responses by examining theory-driven predictors. We will develop and conduct a probability-based nationally representative survey in which we communicate mammography evidence using the current best practices in risk communication, and identify theory-driven predictors of REDS responses, and identify consequences of these responses for decision-making and trust.

II. Background and Significance:

A1. Screening recommendations have changed considerably over recent years.

Breast cancer is the second leading cause of cancer death among women in the U.S., and early detection can result in a cure before it spreads. For many years mammography was strongly promoted, with the aim of maximizing screening uptake.¹⁰⁻¹² However, mammography guidelines have changed considerably as a result of accumulating evidence showing that screening has less benefit for some populations of women, and can cause harm.¹³⁻¹⁵ Harms include false positive results requiring follow-up tests and biopsies, and overdiagnosis—the diagnosis of asymptomatic cancer that will not cause symptoms or harm in a person's lifetime—and resultant overtreatment.¹⁶⁻¹⁸ Although routine mammography is still strongly recommended for women in specific age ranges

and with certain risk factors, many expert groups, including the United States Preventive Services Task Force (USPSTF) and the American Cancer Society (ACS), have de-intensified screening recommendations and expanded the role of informed choice.^{2,4} Most guidelines now emphasize that women should receive balanced information about the benefits and harms of mammography so that they can engage in shared decision making (SDM) and make an informed choice with their doctor about when to start, when to stop, and how frequently to screen.¹⁹

A2. A balanced presentation of both screening benefits and harms is very different from previous unequivocal recommendations to screen, and can strongly contradict women's preexisting beliefs. Controversies about breast cancer screening continue to receive attention in the news media but many women are still unaware of the evidence.^{20,21} Most women greatly overestimate their lifetime breast cancer risk,²² and overestimate their risk even after they have been counseled on their objective risk.²³ A recent systematic review found that in 8 of 9 studies reviewed, a majority (i.e. >50%) of women overestimated the benefit of mammography.²⁴ Most people (women and men) have little or no prior knowledge of harm from overdiagnosis, which is a counterintuitive concept that contradicts common beliefs about how cancer grows and spreads.^{5,25-28} In a 2016 survey, only 16% of women were aware of overdiagnosis as a harm of mammography.⁶ Screening is rarely discussed in clinical encounters in a balanced way; for example, in one survey only 19% of women reported that their provider had discussed the harms of screening in addition to the benefits.²⁹ The public is also very enthusiastic about cancer screening.^{10,30,31} For example, in a recent study we found that 43% of women and men expressed a desire for breast/prostate cancer screening even if it would not reduce the chance of cancer death or extend the length of life.³⁰

A3. Mammography evidence and revised guidelines can be emotionally charged. *"It feels like just when it became okay to talk about breasts and screening, and we convinced insurance to pay for it, and we started getting it to low income women, now we're told that it's maybe not that great and it should be a choice. How are we supposed to believe that?"* (personal communication with PI [name]). Given that many women overestimate their breast cancer risk and the benefits of screening, are unaware of the harms of screening, and are very enthusiastic about screening, it should come as no surprise that mammography evidence and the recommendation for informed choice can elicit negative reactions. Qualitative research has shown that some women are suspicious and resistant to screening evidence, particularly the notion of overdiagnosis.³² In a 2016 U.S. survey less than 1-in-4 women thought both overdiagnosis and overtreatment were "believable".⁶ The notion of risk-based screening—that is, creating a screening plan tailored to a woman's objective cancer risk—is concerning for some women, and can raise suspicions of healthcare rationing.²⁰ In a recent study, women rated a leaflet that described the balance of benefits and harms as less helpful than one that promoted only the benefits, which the authors interpreted as potentially indicating a reluctance to accept information about harms.³³ In recent focus groups involving 42 U.S. adults, participants placed enormous value on cancer screening and expressed hostility toward guidelines suggesting doing less screening.³⁴ Recently we conducted 16 patient interviews in anticipation of this proposal in which we showed women a breast cancer screening decision support tool³⁵ and asked how they felt about the benefits and harms presented. Here is how one woman responded to the idea of harm from overdiagnosis: ***"I think this might give people a false sense of security. Like it's giving them permission to not do screening. So I don't think that this is reassuring, and I don't think it accurately represents the actual risk. This whole thing kinda makes me mad. I find it very frustrating because it, it feels like...it feels like propaganda."***

Altogether, the weight of the evidence suggests that communicating mammography screening evidence can elicit negative reactions. The types of negative reactions that we are particularly concerned about include **Reactance** (i.e. perceived manipulation or influence, e.g. "this is trying to ration healthcare"), **self-Exemption** (e.g., "this doesn't apply to me"), **Disbelief** (e.g., "you can't believe all the research anyway"), and **Source derogation** (e.g., "I don't trust this source"), which we shorten to **REDS**.^{8,9} These responses are sometimes referred to collectively as "defensive coping",³⁶ although we prefer "REDS" to refer directly to the four types of responses. To date, no research has examined REDS systematically to assess their prevalence and causes in the context of communicating mammography screening evidence. And even though many women

react negatively to screening information, many women also want to be informed and be able to make a choice.³⁷ The result is a delicate situation in which there is need to convey the evidence to women, but also a need to do it in a way that maintains credibility and trust.

III. Preliminary Studies/Progress Report:

IV. Research Methods

A. Outcome Measure(s):

The primary outcome measures in this survey are REDS responses and screening intentions. See Table 1 below for all survey measures.^{35,55,56,61,66,72,96-99}

	Measure description	Source
Primary DVs	REDS responses	See appendix
	Screening intentions	Schapira et al. 2019
Secondary DVs	Change in trust in provider and healthcare system, pre vs. post BCS-DA	Egede et al. 2008
	Positive responses, e.g. appreciation of information	Ad hoc
	Change in screening knowledge, pre vs. post BCS-DA	Schapira et al. 2019
IVs: primary	Breast cancer risk perceptions: affective, deliberative, experiential	Ferrer et al. 2016
	Perception of net screening benefit (benefits minus harms) at pre-test	[name] et al., 2018
	Objective breast cancer risk	Schapira et al. 2019
	Cognitive responses to information	See appendix
	Medical Maximizing-Minimizing orientation	[name] et al., 2016
	Perceived norms	Hersch et al., 2015
	Past screening experience	Petrova et al., 2015
Secondary IVs and control variables	Perceived barriers to screening	Hyman & Baker 1992
	Friends/family experience with breast cancer	Petrova et al., 2015
	Subjective numeracy	Fagerlin et al., 2007
	Health literacy	Chew et al., 2008
	Demographics	Standard questions

Table 1. Aim 1 measures.

B. Description of Population to be Enrolled:

Inclusion:

- Female
- Between 39-49 years of age
- No history of breast cancer
- No known BRCA1/2 mutation

Exclusion:

- Non-English or Spanish Speaking
- Persons unable to provide informed consent (e.g. severe dementia or cognitive disability or illiterate)
- History of breast cancer
- Known BRCA1/2 mutation

Pilot Survey: We will pilot test questions to measure REDS and cognitive reactions to assess item variability, internal consistency, and reduce the total number of items. We will recruit 700 women through Dynata. Dynata manages an online participant panel of millions of adults across the United States. Participants who are part of Dynata's panel have agreed to participate in surveys in exchange entry into lotteries for small cash prizes.

Pilot Interviews: We will recruit up to 15 women from [name]'s Internal Medicine clinic at UCHealth. These interviews will focus on assessing overall knowledge and understanding of the information presented in the decision aid. Participants will receive a \$25 gift card for participating in the interview.

Nationally Representative Survey: We will recruit 700 women age 40-49 through Ipsos Public Affairs. Ipsos manages an online participant panel allowing population inferences using probability sampling methods and providing Internet access to households that do not have it.

Nationally Representative Interviews: We will recruit up to 40 women from the Ipsos survey who agreed to be contact for a follow-up phone interview. We will specifically recruit women who expressed negative reactions to mammography evidence, so that we can assess how to improve the BCS-DA using insights from those who were negatively affected. We will attempt to recruit at least 25% non-White participants for these interviews.

C. Study Design and Research Methods

The survey flow is displayed in the figure below and will unfold as follows: First, women will be asked premeasure questions displayed in the figure below. Second, women will learn their objective cancer risk estimate, and will report their affective, deliberative and experiential risk perceptions.⁵⁶ Third, women will react separately to the three distinct components of mammography evidence (benefits, false positives, overdiagnosis). The purpose of assessing reactions to each component of the evidence is to identify how positively or negatively each part is received. We anticipate that overdiagnosis may be received most negatively. Measured reactions will include REDS responses, and cognitive reactions as previously described (i.e. whether the information is compatible or not with other knowledge). Finally, after all of the information has been presented, women will provide overall reactions to the evidence using the same measures. Next women will report overall positive responses, e.g., the extent to which they appreciated receiving the information, felt empowered by it, and

want to talk to their provider about it. Lastly, women will repeat some of the pre-measures (e.g. knowledge, trust) and report demographics and individual differences.

Pilot Survey: Recruitment and survey distribution will be done by Dynata. All data will be collected electronically using Qualtrics.

Nationally Representation Survey: Recruitment and survey distribution will be done by Ipsos. All data will be collected electronically using Qualtrics.

All Interviews: Patients will be invited to schedule a phone call for the interview (using a regular phone or using Zoom), and audio will be recorded and transcribed.

D. Description, Risks and Justification of Procedures and Data Collection Tools:

Benefit from participating in the research cannot be claimed. Women will learn about mammography benefit and harm, which may lead to more informed screening decisions. Learning how to help communicate more effectively about counterintuitive and surprising medical evidence is an area in great need of attention. The intervention is designed to improve communication and decision quality and enhance the overall decision making. Given that the risks are minimal and the benefits great (to both patients, clinicians, and society as a whole) we believe that the benefits of the proposed project outweigh any risks.

E. Potential Scientific Problems:

The length of the survey may be an issue since we are recruiting through Ipsos.

There is a possibility that not a sufficient amount of subjects with voluntarily self-identify for the follow-up interviews.

F. Data Analysis Plan:

Pilot Survey: We will check the variability of each questionnaire item to assess suitability for exploratory factor analysis. Exploratory factor analysis will be used to identify the factor structure of the REDS items. Items that do not load onto any factor will be dropped. Reliability of the remaining items

Nationally Representative Survey: Summary statistics will estimate the prevalence of REDS to each part of the BCS-DA. Simple within-subjects tests (e.g. ANOVA) will compare REDS in response to screening benefits, false positives, and overdiagnosis.

All Interviews: We will conduct exploratory content analysis of these qualitative interviews using the analytic program Dedoose to extract themes in patients' reactions to the presented information.

Safety Oversight:

The principal investigator will be responsible for the conduct of this study, overseeing participant safety, executing the data and safety monitoring (DSM) plan, and complying with all reporting requirements to local and federal authorities. This oversight will be accomplished through additional oversight from the Data and Safety Monitoring Committee (DSMC) at the University of Colorado Cancer Center (CU Cancer Center). The DSMC is responsible for ensuring data quality and study participant safety for all trials at the CU Cancer Center. A summary of the DSMC's relevant activities is as follows:

- Conduct of internal audits

- Has the authority to suspend studies for safety or conduct issues
- May submit recommendations for corrective actions to the CU Cancer Center's Executive Committee

Study audits conducted by the DSMC will consist of a review of the regulatory documents, consent forms, and source data verification. Documentation of the audit conducted by the DSMC will then need to be submitted to the IRB of record at the time of the IRB's continuing review of this trial (if applicable).

G. Summarize Knowledge to be Gained:

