### Data collection procedures

Participants will be recruited through Ipsos.

*No files selected*

Sample size

Our expected sample size is 500 participants.

Sample size rationale

The study was powered to detect an interaction between objective cancer risk and REDS on receipt of screening (Aim 2). We estimated power by simulation based on 2000 data sets using R statistical software. We use a logistic regression model for the outcome of screening (yes/no) with fixed effects for REDS (high/low) and objective cancer risk (continuous) and their interaction. Assuming that there is a probability of 50% of high REDS (treated as a binary variable), a sample size of 500, and that 10% of variability is explained by other factors in the model (confounders), we would be able to detect a difference in the log odds of -0.3 with 90% power (alpha=0.05). Thus, if the odds of the outcome is 1 in the low REDS group, for every unit increase in cancer risk we can detect an odds of 0.74 (=exp(0-0.3)) in the high REDS group (i.e., an odds ratio of 1.35). Additionally for the outcomes in Aim 1, with a sample size of N=500 we will be able to estimate the prevalence of REDS with a margin of error of 2.8-3.0% depending on the actual prevalence 30-70%. The sample size of 500 will also allow us to detect an increment of 1.2% in variability explained in the linear regression models assuming other factors explain 20% of the variability with 80% power (alpha=0.05).

Stopping rule

We have contracted with Ipsos to collect 500 participants.

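### The protocol recruits 700 women to the Ipsos survey and the SAP collects 500, with nothing linking the two; the SAP's margin of error fits neither number at 95% confidence

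*Protocol*

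**What the plan says.** Protocol, section IV.B (Description of Population to be Enrolled), on the nationally representative survey: "We will recruit 700 women age 40-49 through Ipsos Public Affairs". The same section describes a separate pilot survey on another panel: "We will recruit 700 women through Dynata". The protocol gives no rationale for either 700.

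SAP, Sampling Plan, Data collection procedures: "Participants will be recruited through Ipsos", which identifies the national survey rather than the pilot. It continues: "Our expected sample size is 500 participants". Under the stopping rule: "We have contracted with Ipsos to collect 500 participants".

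The SAP's sample size rationale makes three claims at 500:
- 90% power for an interaction of -0.3 on the log-odds scale between objective cancer risk and REDS (high or low);
- a margin of error of 2.8-3.0% for REDS prevalence between 30% and 70%;
- 80% power for a 1.2% increment in explained variance when other factors explain 20%.

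**The concern.** The sample size and the stopping rule together define when data collection is complete. By the protocol's number, closing at 500 is a shortfall of 200 women. By the SAP's, it is the planned end. An auditor comparing enrolment with the protocol would record under-enrolment, while an analyst working from the SAP would see none.

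The precision statement is a second problem in the same paragraph of the SAP. Estimating REDS prevalence is part of Aim 1, and the margin of error tells a reader how exact that estimate will be. The stated margin is too narrow for either sample size at the conventional confidence level, so settling the number will not by itself repair it.

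**Working it through.** **1. Is it the same survey?** Both documents name Ipsos. The Dynata pilot is a separate survey with its own 700, so it does not explain the gap.

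**2. Does anything connect 700 to 500?**
- Going from 700 to 500 is a loss of (700 - 500)/700 = 28.6%. No completion, attrition or exclusion rate appears in either document.
- The SAP's Data exclusion section removes women who fail both attention checks, but gives no percentage and no inflation of the sample. Its 500 is the number to be collected, before those exclusions.
- Section IV.B of the protocol marks the interview numbers (15 and 40) as ceilings. The 700 is not marked in that way.

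**3. Which number do the SAP's calculations use?** The explained-variance claim can be checked. Inputs from the SAP: increment 0.012, other factors 0.20, alpha 0.05. One tested degree of freedom is assumed.
- f² = 0.012/(1 - 0.20 - 0.012) = 0.01523; noncentrality = f² × N.
- N = 500: noncentrality 7.6, power 78.6%. The increment detectable with 80% power is 1.24%, which rounds to the stated 1.2%.
- N = 700: noncentrality 10.7, power 90.3%. The detectable increment is about 0.9%.

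This claim reproduces at 500, within 2 points of the stated 80%, and not at 700.

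**4. The interaction claim.** This cannot be confirmed or refuted, because the SAP gives neither the standard deviation (SD) of objective risk nor the baseline outcome rate. Assumptions used here: normally distributed risk, baseline odds of 1, half of women with high REDS, variance inflated by 1/(1 - 0.10) for confounders, two-sided alpha 0.05.

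| Assumed SD of risk | Power, N = 500 | Power, N = 700 |
|---|---|---|
| 1.0 | 35% | 46% |
| 1.5 | 63% | 78% |
| 2.0 | 85% | 94% |
| 2.5 | 95% | 99% |

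An SD of about 2.2 gives the stated 90% at 500. The same inputs give about 97% at 700.

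**5. The margin of error.** Formula: z × √(p(1 - p)/N), with z = 1.96 for 95%. It is symmetric around p = 0.5, so p = 0.3 and p = 0.5 bound the range from 30% to 70%.
- N = 500: 1.96 × √(0.21/500) = 4.02%; 1.96 × √(0.25/500) = 4.38%.
- N = 700: 1.96 × √(0.21/700) = 3.39%; 1.96 × √(0.25/700) = 3.70%.
- Sample size for the stated margins at 95%: 1.96² × 0.21/0.028² = 1,029; 1.96² × 0.25/0.030² = 1,067.
- Confidence that the stated margins represent: about 82-83% at N = 500 and about 89% at N = 700.

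**The case against.** The strongest reply is that recruiting and collecting are different things: 700 could be an approved ceiling or a recruitment number, and 500 the completes. Neither document excludes this, so it cannot be said that 700 is proved to be an error. Nor can it be said that it was carried over from the pilot, although the coincidence invites that guess. But neither document states such a relation, and if it was intended it needs to be written down.

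A second reply is that the SAP is consistent with itself. For the analysis plan that is true, but it does not settle a conflict with the protocol.

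A reader might also infer four stronger things, none of which the documents support:
- *That the planned end of collection is unknown, or that 500 would be early stopping.* The SAP's stopping rule states the end, and its interim weekly summaries exclude inferential statistics.
- *That the study is underpowered.* The SAP's power claims are made at 500. The explained-variance claim reproduces there, and the interaction claim cannot be tested without the missing inputs.
- *That 700 women would invalidate the power claims.* They would become conservative. Only the stopping rule would be contradicted outright.
- *That the inclusion criterion "Between 39-49 years of age" contradicts the survey's 40-49.* The inclusion list covers four components, and a narrower range for one of them is compatible with it. At most this needs clarifying, and it has no bearing on the sample size.

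**Conclusion.** The point holds as an inconsistency between documents and a wrong precision figure. The sample size conflict rests on the text alone and needs no assumption. The figure of 500 is the better supported: it is contracted, it is the stopping rule, and the SAP's calculations are stated at it. That is a reason to prefer it and falls short of proof that it is the intended number.

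The precision finding assumes 95% confidence and simple random sampling, since the SAP states neither a level nor a design effect. On those terms the SAP understates the margin by about 1.2 to 1.4 percentage points at 500 (4.0 - 2.8 and 4.4 - 3.0) and by about 0.6 to 0.7 at 700 (3.4 - 2.8 and 3.7 - 3.0). The choice between 500 and 700 itself moves the true margin by only about 0.6 to 0.7 of a point.

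**What to change.** 1. Reconcile the protocol and the SAP to one sample size for the national survey. Unless the sponsor confirms otherwise, amend section IV.B of the protocol to 500. Alternatively, state there that 700 is a recruitment number expected to yield 500 completes, and give the rate assumed.
2. In the SAP's sample size rationale, restate the margin of error at the confirmed number and name the confidence level: 4.0-4.4% at 95% for 500 women, or 3.4-3.7% for 700.
3. If the confirmed number is not 500, update the stopping rule and the power statements to match.

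With 500 confirmed, the cost is a short text change in each document and no additional participants. If 700 is the intended number of completes, the contract with the panel provider would also have to change.

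### No weighting or design-based variance is specified for a REDS prevalence presented as national, and the SAP's stated 2.8 to 3.0 point margin is narrower than even simple random sampling gives

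*Protocol*

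**What the plan says.** Protocol section I (Aim 1) puts the prevalence of REDS first among its objectives and plans a "probability-based nationally representative survey". Section IV.B describes the vendor's resource as an online "panel allowing population inferences using probability sampling methods", so the stated target is a population and not a set of respondents.

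For the national survey, the analysis plan in section IV.F has two sentences: "Summary statistics will estimate the prevalence of REDS to each part of the BCS-DA", and "Simple within-subjects tests (e.g. ANOVA) will compare REDS in response to screening benefits, false positives, and overdiagnosis".

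Under Statistical models, the SAP lists correlations, t-tests, and linear and logistic regressions. Its sections on Transformations, Inference criteria, Data exclusion and Missing data do not mention weights. In the text supplied, neither document refers to selection or post-stratification weights, non-response adjustment, a design effect or design-based standard errors.

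The only precision statement is in the SAP's Sample size rationale: a margin of 2.8 to 3.0 points at N=500, for a true prevalence between 30% and 70%. It gives no formula and no confidence level. The documents also differ on sample size. The SAP says "Our expected sample size is 500 participants"; Protocol section IV.B says "We will recruit 700 women age 40-49 through Ipsos Public Affairs".

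**The concern.** A probability panel supports inference to a population only if the analysis reflects how women were selected and who responded. The plan does not say how it will do this, so whether to weight, and with which weights, remains open until after the data are seen.

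The plan itself gives reasons why composition could matter. SAP hypothesis SH1 expects REDS to vary with trust in the healthcare system, medical maximizing and prior screening use. SH2 expects more self-exemption among Black than White women. Protocol section IV.E names survey length as a possible problem, and the SAP excludes women who fail both attention checks. If response, completion or exclusion is related to these characteristics, the respondents' prevalence differs from the national one.

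Prevalence is the Aim 1 result that depends most directly on representativeness. A reader will also judge its reliability by the margin in the SAP, and that margin looks too small for the stated N.

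**Working it through.** **Inputs from the documents.** N=500 (SAP, Sample size); N=700 (Protocol IV.B); prevalence p from 0.3 to 0.7; stated margin 2.8 to 3.0 points (SAP, Sample size rationale). The confidence level is not stated. I assume 95%, because the adjoining power statements use alpha=0.05.

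**Assumed input.** A design effect (DEFF) of 1.0 to 2.0. The documents give none. A value of 1.0 corresponds to an equal-probability draw that needs no weighting.

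**Step 1: try to reproduce the stated margin.** Half-width = z × sqrt(p(1−p)/N).

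- N=500, 95%, p=0.3 or 0.7: 1.96 × sqrt(0.21/500) = 4.02 points.
- N=500, 95%, p=0.5: 1.96 × sqrt(0.25/500) = 4.38 points.
- A Wilson interval gives 4.0 to 4.4 points.
- N=500, 90%: 3.37 to 3.68 points. N=500, 80%: 2.63 to 2.87 points.
- N=700, 95%: 3.39 to 3.70 points. N=700, 90%: 2.85 to 3.11 points.

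None of these matches 2.8 to 3.0.

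**Step 2: what would the stated figure imply?** At N=500, 2.8 points at p=0.3 corresponds to 82.8% confidence, and 3.0 points at p=0.5 to 82.0%. At 95% confidence the required N is 1.96² × 0.21/0.028² ≈ 1,029 and 1.96² × 0.25/0.030² ≈ 1,067. Against 4.02 and 4.38, the stated margin is about 30% too narrow (2.8/4.02 = 0.70; 3.0/4.38 = 0.68) before any design effect.

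**Step 3: allow for weighting.** Half-width = 1.96 × sqrt(DEFF × p(1−p)/N), and effective N = N/DEFF. Margins are in points, for p=0.3 to p=0.5.

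| DEFF (assumed) | Effective N of 500 | Margin, N=500 | Margin, N=700 |
|---|---|---|---|
| 1.0 | 500 | 4.0 to 4.4 | 3.4 to 3.7 |
| 1.3 | 385 | 4.6 to 5.0 | 3.9 to 4.2 |
| 1.5 | 333 | 4.9 to 5.4 | 4.2 to 4.5 |
| 2.0 | 250 | 5.7 to 6.2 | 4.8 to 5.2 |

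If a weighted estimate were reported with simple-random-sampling errors, a nominal 95% interval would cover about 89.0% at DEFF 1.5 and 83.4% at DEFF 2.0, ignoring bias.

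**Step 4: what bias could look like (illustration only).** Suppose a group is 30% of the population but 20% of respondents, with prevalence 50% against 30% elsewhere. The unweighted estimate is 0.20 × 50 + 0.80 × 30 = 34%, and the population value is 0.30 × 50 + 0.70 × 30 = 36%. The shift is 2 points, which is the 10-point difference in share times the 20-point difference in prevalence. None of these shares or prevalences comes from the documents.

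**The case against.** The strongest reply is that the plan is under-specified, not wrong. A weighted proportion is still a summary statistic, and nothing in either document rules out vendor weights. A reader might infer that the sponsor has chosen unweighted estimates, but the documents only leave weighting unmentioned. That part of the reply stands.

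A reader might also infer that the intervals will be too narrow because the variance added by weighting is left out. This does not follow. An unweighted estimator does not incur that variance, and its problem would be bias. Under-coverage arises only if a weighted estimate is paired with simple-random-sampling errors, which the documents do not say is planned. Nor is the SAP's margin a simple-random-sampling margin at 95% that merely lacks a design effect: as shown above, it falls short of that too.

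The reply also points out that every design effect and bias figure is assumed, that the illustrative 2-point shift is smaller than the 4.4-point sampling margin, and that the SAP's numbered hypotheses concern associations, group differences and pre-post change, not prevalence. All of this is true, and it limits the reach of the point. It does not remove it. Bias from composition does not shrink as N grows, prevalence is a named part of Aim 1, and raking on the collected demographics is possible but not planned.

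**Conclusion.** The point holds in two parts.

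First, a national prevalence is promised without any stated means of getting from respondents to the nation. Taken literally, the plan yields a prevalence among respondents that may be biased for eligible US women aged 40 to 49. The documents do not allow the size of that bias to be computed. It could be small if selection was equal-probability and non-response little related to REDS.

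Second, the stated margin is too narrow whatever is decided on weights. At N=500 and 95% confidence it should be 4.0 to 4.4 points, not 2.8 to 3.0. At N=700 it would be 3.4 to 3.7. With assumed design effects of 1.0 to 2.0, the range at N=500 is 4.0 to 6.2 points. This part rests on 95% being the intended level. The stated figure would be about right at 82% to 83% confidence, but the SAP does not say that such a level was meant.

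The plan should be changed before analysis. The point does not show that the association tests in H1 to H5 are invalid.

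**What to change.** - **Prevalence and component comparison:** estimate both with the vendor's base and post-stratification weights, or with weights raked on the collected demographics, and use design-based standard errors. Name the weights in the SAP before analysis.
- **H1 to H5:** keep the unweighted models as primary and add a weighted sensitivity analysis.
- **Precision statement:** replace 2.8 to 3.0 points in the Sample size rationale with a corrected margin, stating the confidence level, the assumed design effect and the effective N.
- **Sample size:** reconcile the Protocol's 700 with the SAP's 500 and use one figure throughout.

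If weights cannot be obtained or built, the alternative is to drop the national claim and describe the results as those of respondents.

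The cost is a weight variable in the data delivery and survey procedures in the code. The downside is wider intervals and a less favourable stated margin.
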